# Analysis of outcomes:

Hypothesis will be tested using a two factor (3 beverages x 4 times) repeated measures ANCOVA on change scores (Times 4, 3 and 2 minus Time 1 are the 4 Times). The primary interest will be whether there is a statistically significant main effect for time or interaction. Focused contrasts between specific time points as follow up tests.

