The effects of E+shots on mood, cognitive function, heart rate, blood pressure, cortisol and fine motor task performance NCT #16-05

*Design:* This is a double blinded cross-over experiment with repeated measures on treatment (25mg caffeine vs 100mg caffeine vs e+shots) and Time (Time 1 (pre-beverage), Time 2, Time 3, Time 4). Previous night's sleep and occupation may be used as a co-variate in the statistical analysis.

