#### Procedure:

### Screening day:

- Potential subjects will complete an initial online screening using questionnaires that will be posted on surveymonkey.com. The appendices listed below are the questionnaires that are posted in the survey.
- The survey may be accessed through the tiny URL, QR code, or through a link that will be provided by the researcher.
  - o Appendix G- A demographic and medical history questionnaire
    - As seen in the exclusion criteria all subjects who use prescription or over the counter medications for chronic medical conditions will not be allowed to participate in the study, with the exception of people taking oral contraceptives.
    - Subjects who are taking a prescription or over the counter medication for an acute health condition may be asked to participate in the study after they are no longer taking the medication or they will be given the option to drop out of the study.
  - Appendix H- Profile of Mood Survey (POMS) brief form
    - We will calculate the energy score of the POMS.
    - If the energy score is >=13 then the potential subject will be eliminated from the study
  - o Appendix I- Caffeine consumption questionnaire
    - Using the data from this survey subjects who consume >=200mg of caffeine per day will be eliminated from this study
  - Appendix J- Food frequency questionnaire
    - Using the data from this survey subjects who consume >=150 servings of polyphenols per month will be eliminated from the study
  - Appendix K- Mental and Physical State and Trait Energy and Fatigue Scales (see appendix R for approval to use questionnaire)
    - The objective of this scale is to control of cognitive bias by asking questions regarding use of prescription drugs and using a different energy and fatigue scale to measure energy levels.
    - A score of >10 on the energy scale will eliminate the potential subject
    - This scale also measures physical and mental activity levels which will be used in the statistical analysis as covariates
  - Appendix L- Pittsburgh sleep quality index
    - This survey will be used to measure sleep time and sleep quality of potential subjects.
    - Sleep will be used to determine eligibility on day of testing
    - Sleep quality will be used as a covariate in the statistical analysis
- After completion of survey, a research assistant will verify that the subject is eligible for the study and will contact them via the email that is provided by the subject.

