### Days 2-4

Testing days 2-4 will be similar except subjects will consume a different beverage daily (list the 3 different beverages). To reduce bias, the days that subjects will consume a certain beverage will be randomized using a randomizing software on randomizer.org. All beverages are labeled as products, A, B or C and are blinded for the researcher. Information regarding all beverages is listed in Table 1.

On each day subjects will complete the following procedure:

Subjects will complete a pre-screening questionnaire on each day. The questionnaire will contain the following surveys

- Appendix M- 24 hour drug/medicine/supplement recall
  - This survey asks for a 24-hour prescription medication, over the counter medication, and supplement recall. Because of the potential for cognitive bias (as described above) we are asking the subjects for the names of any medications they may be taking. In our past studies there were a few subjects that initially reported that they were not taking any prescription or over the counter medications (either for a chronic or acute health condition) however, during the daily testing procedures when we asked these subjects specifically what medications they were taking they listed certain medications. By asking specifically what medications the subjects are taking we are hoping to reduce the risk of cognitive bias and appropriately eliminate subjects who are taking prescription or over the counter medications while they are in the study.
    - The survey asks if subjects are taking an oral contraceptive and specifically what the name of the oral contraceptive is. The information on the specific type of oral contraceptive is needed as certain oral contraceptives have an impact on mood while others do not (Kahn & Halbriech, 2005).
  - We are also asking for caffeine intake and time of intake. To control for cognitive bias we are asking for time of intake.
- Appendix N- Sleep questionnaire
  - o This survey will be used to determine the amount of sleep the subject had the night before.
  - This survey will serve two purposes
    - If subjects had > or < ±2 hours of sleep from their normal sleep then they will be rescheduled. Their normal sleep will be determined using Appendix L. Their normal sleep will be given to the researcher in charge of collecting data prior to subject's arrival.

- If the subject is eligible for the study, the sleep may be used as a covariate in the data analysis.
- Appendix Q- What I ate today

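### Subjects may be eliminated after one or two beverage sessions, but no analysis set is stated, and the named ANCOVA as usually fitted would discard those sessions

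*Combined protocol and SAP*

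**What the plan says.** The opening Design paragraph describes a "double blinded cross-over experiment with repeated measures on treatment". Under Days 2-4, "subjects will consume a different beverage daily", and "the days that subjects will consume a certain beverage will be randomized". A complete subject therefore contributes three sessions. Table 2 gives each session four 36-minute batteries, one before the beverage and three after it.

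The Appendix M recall is repeated on every test day. One stated aim is to "appropriately eliminate subjects who are taking prescription or over the counter medications while they are in the study". The same paragraph reports that, in the team's past studies, a few subjects disclosed medication only once daily testing had begun. A night's sleep too far from normal is handled differently: "then they will be rescheduled".

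Analysis of outcomes names one model, a "two factor (3 beverages x 4 times) repeated measures ANCOVA on change scores". The stated interest is "whether there is a statistically significant main effect for time or interaction". The plan does not say which subjects or sessions are analysed, how the model is estimated, whether removed subjects are replaced, or what happens to sessions completed before removal.

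**The concern.** A subject eliminated at the Day 3 recall has completed one session, and at the Day 4 recall two. The classical least-squares repeated measures ANCOVA, with beverage and time both within subject, needs every beverage-by-time cell and omits anyone with an empty one. A subject with two beverages completed would then contribute nothing, not even to the comparison of those two.

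Two things are at stake. The first is precision, which is lost whatever the reason for leaving. The second is bias. If subjects who do badly on one beverage tend to leave afterwards, completers-only analysis deletes those poor results and that beverage looks better than it is. Because the plan is silent, the choice between completers and all sessions could also be made after the data are seen.

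**Working it through.** **Inputs.** From the documents: three sessions per subject, randomised order, and possible removal at each day's recall. The documents give no sample size, SD, loss rate or correlation, so there is no stated figure to reproduce. Assumed: a loss q before Day 3 and again before Day 4; a correlation ρ of 0.1 to 0.5 between a subject's change scores on different days; six equally likely orders; one averaged change score per session with SD 1.

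**Step 1: what completers-only analysis discards.** The shares of subjects with one, two and three sessions are p1 = q, p2 = q(1−q) and p3 = (1−q)². The share of completed sessions discarded is (p1 + 2p2)/(p1 + 2p2 + 3p3).

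- q = 5%: p3 = 0.9025, so 9.8% of subjects are excluded. Sessions discarded: 0.145/2.8525 = 5.1%.
- q = 10%: p3 = 0.81, so 19.0% of subjects are excluded. Sessions discarded: 0.28/2.71 = 10.3%.

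**Step 2: precision.** Under exchangeable correlation, generalised least squares gives the variance ratio for a two-beverage contrast, all sessions against completers only, as

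p3 / [p3 + p2(2 − ρ/(1+ρ))/3 + p1(1−ρ)/3].

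Example with q = 10%, ρ = 0.5: 0.81/(0.81 + 0.09 × 0.5556 + 0.10 × 0.1667) = 0.81/0.8767 = 0.924.

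| q | ρ = 0.1 | ρ = 0.3 | ρ = 0.5 |
|---|---|---|---|
| 5% | 0.952 | 0.958 | 0.963 |
| 10% | 0.903 | 0.914 | 0.924 |

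The variance reduction is about 4-5% at q = 5% and 8-10% at q = 10%. With balanced orders, adding a test-day term leaves these ratios unchanged.

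**Step 3: bias.** These are simulations with no true beverage difference.

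| Assumed reason for leaving | Completers only (SD) | All sessions, likelihood (SD) |
|---|---|---|
| Unrelated to beverage or response (10% per interval) | −0.001 | −0.002 |
| Depends on beverage only (20% after one, 5% after the others) | −0.005 | +0.001 |
| Poor response to one beverage (40%, otherwise 5%) | +0.049 | +0.003 |
| 25-50% of the worst 20-30% on the 100 mg day only (3-10% of subjects lost) | about +0.02 to +0.12 | within about 0.007 of zero |
| 25% of the worst 20%, or 50% of the worst 30%, after every beverage alike (9% and 27% lost) | 0.000 and 0.005 | not needed |

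The first three rows use 20,000 subjects and ρ = 0.5, with a standard error of about 0.0075 SD for the all-sessions estimate. Material bias appears only where leaving depends on response and does so differently between beverages.

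**Step 4: the test-day term.** Removal takes away later sessions, so drift over days matters. With an assumed drift of 0.3 SD per day, an all-sessions model without a test-day term gave a spurious difference of about 0.02-0.04 SD. Adding the term brought it to about 0.006 SD or less.

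**The case against.** A reader might infer that the plan restricts the analysis to completers. It does not say so. That is how the named method is usually fitted, and a mixed-model fit would keep partial subjects. What stands is that nothing in the plan settles the matter.

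A reader might also infer that any loss related to a beverage biases the comparison. In a within-subject contrast it does not: loss depending only on which beverage was taken gave about zero, as did response-dependent leaving that was equal across beverages. The one documented elimination rule works on reported medication, is applied before that day's beverage, and has no stated link to response. Medication taken after a poor session, or voluntary withdrawal, could create a link, but neither is described. The simulated bias also assumes that the analysed outcome itself drives leaving. If a different outcome drives it, with correlation 0.3-0.5, a worst case of 0.09 SD falls to 0.03-0.05 SD.

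Other apparent support is weak. The sentence "they will be given the option to drop out of the study" sits under Screening day and concerns acute medication at entry, so it says little about loss between test days. Sleep deviations lead to rescheduling, which preserves complete data. No section describes a missed battery within a session.

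Finally, a disclosure on Day 3 or 4 may reveal that the subject was already on medication at an earlier session, and one could argue that the session should then go. That is a fair question of analysis set, but it too needs a stated rule.

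**Conclusion.** The point holds as a cheap improvement. The plan provides for elimination during the test days, names a model that conventionally drops incomplete subjects, and states no analysis set. The loss of completed sessions needs no assumption about why subjects leave. Its size does: a variance penalty of about 4-10% rests on assumed removal of 5-10% at each of Days 3 and 4 and on correlations of 0.1-0.5.

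Bias is a conditional risk and has not been shown. It was about 0.02-0.12 SD under patterns chosen so that poor responders to one beverage leave, and about zero otherwise. The documents do not support a claim that the beverage comparison will be biased.

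**What to change.** In Analysis of outcomes, specify a likelihood-based linear mixed model with:

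- **Analysis set:** every session with a Time 1 battery and at least one post-beverage battery, expressly including sessions completed before elimination or drop-out.
- **Fixed effects:** beverage, post-beverage time, beverage × time and test day (period), plus the covariates already planned: previous night's sleep and occupation (Design, where they are optional), and sleep quality and physical and mental activity levels (Screening day).
- **Random effects:** subject and subject-by-day.
- **Sensitivity analysis:** the completers-only result.
- **Reporting:** losses by the preceding beverage, with reasons, and a stated rule for a session that a later disclosure puts in doubt.

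The cost is revised wording and minor analysis work in standard software, with no new subjects or data. The downside is the assumption that leaving depends only on recorded data; this is weaker than what a completers-only analysis requires.

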  - o This survey will be used to determine what the subject ate the day of the testing
  - The information may be used during data analysis to estimate methyxanthine intake

After subjects have been pre-screened for the day, the research assistant will collect saliva using the drool down method. To collect data using the drool down method subjects must collect saliva in their mouth and let it drool down through a straw into a 15mL saliva collection tube. After ~2mL of saliva has been collected, saliva will be stored in a chest filled with ice, prior to transportation to a freezer that is set at -80F.

After saliva collection, subjects will go through the following mental energy test battery (see table 2). Consumption of beverages and subsequent mental energy test batteries will be administered as outlined in table 2. *Dependent Variables* 

1) Computerized cognitive battery:

a.	Serial subtraction of the number three	2 minutes
b.	Serial subtraction of the number seven	2 minutes
c.	Continuous performance test (CPT)	5 minutes
d.	Bakan rapid visual processing task	16 minutes

2) Self-reported measures

a.	Motivation to perform cognitive tasks (Appendix N)	1 minute
b.	Visual analog scales of mental energy and fatigue (Appendix O)	1 minute
c.	POMS (Appendix H)	3 minutes

3) Physiological measures

a. Resting heart rate and blood pressure 1 minute

4) Fine motor skills

a. 9-hole peg test 5 minutes

Total time 36 minutes

The 9-hole peg test is used to measure finger dexterity. The test is administered by asking the client to take the pegs from a container, one by one, and place them into the holes on the board, as quickly as possible. Participants must then remove the pegs from the holes, one by one, and replace them back into the container.

After completion of the mental test batteries and procedure outlined in Table 2, subjects saliva will be collected again using the drool down method.

Table 1

Ingredient Name	Current E-shot	Placebo w/ Caffeine	Placebo w/o Caffeine
Water	4oz	4oz	4oz
LERA Herbal Extract Complex	Proprietary	0	0
Green Tea (Camellia sinensis) Leaf Extract (50% Caffeine)	Proprietary	0	0
Yerba Mate Extract (25% Caffeine)	Proprietary	0	0
D-Ribose	25.000 mg	0	0

Synthetic Caffeine	0.000	100.000mg	0
Apple Juice Concentrate 70 Brix	Trace amounts	Trace amounts	Trace amounts
	Trace amounts	Trace amounts	Trace amounts
Glycerin (vegetable source)	Trace amounts	Trace amounts	Trace amounts

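### Analysing change from Time 1 instead of adjusting for that day's Time 1 costs precision in the beverage main effect, in beverage contrasts at a single time and, if saliva is assayed for it, in cortisol's beverage comparison; the plan's primary tests over three change scores are unaffected.

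*Combined protocol and SAP*

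**What the plan says.** The whole analysis is stated under Analysis of outcomes: a two-factor "repeated measures ANCOVA on change scores (Times 4, 3 and 2 minus Time 1 are the 4 Times". It defines three differences but counts four times. On which tests matter it says: "The primary interest will be whether there is a statistically significant main effect for time or interaction". The follow-up is "Focused contrasts between specific time points as follow up tests". The beverage main effect is not singled out.

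The covariates are named elsewhere. The Design paragraph allows the previous night's sleep and occupation. The Screening day section adds physical and mental activity, and "Sleep quality will be used as a covariate in the statistical analysis". Days 2-4 again allows the previous night's sleep. Time 1 is never listed, so ANCOVA here does not mean adjustment for baseline.

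The pre-beverage score is available for every test day. Days 2-4 says "On each day subjects will complete the following procedure", and Table 2 places one full battery before the beverage and three after it.

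Cortisol appears in the title, "The effects of E+shots on mood, cognitive function, heart rate, blood pressure, cortisol and fine motor task performance", but not in the list of dependent variables. The only biological samples described are two saliva collections per test day. The first comes before any testing: "After subjects have been pre-screened for the day, the research assistant will collect saliva using the drool down method". After the last battery, "subjects saliva will be collected again using the drool down method".

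**The concern.** In a cross-over every beverage comparison is made within the participant. The slope that matters is therefore how far a day's post-beverage score follows that same day's Time 1, once the participant's usual level is removed. A change score sets this slope to 1. If the true slope is lower, subtraction adds noise from Time 1 to the comparison. A fitted slope does not.

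The title asks what E+shots does to several outcomes. A beverage effect of similar size at Times 2, 3 and 4 shows in the beverage main effect and in beverage contrasts at each time, and these are the estimates that lose precision.

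The screening covariates do not help. Sleep quality and activity have one value per participant, so as additive terms they cannot reduce within-participant error. Test-day sleep does vary by day, but it is optional and is no substitute for the Time 1 score.

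**Working it through.** **Inputs.** From the documents: three beverages in a cross-over, Time 1 plus three post-beverage batteries per day, two saliva samples per day. The documents give no sample size, SD, correlation, effect size, alpha or power, so there is no stated figure to reproduce. Assumed: within-subject variance 1 at every time; rho, the within-subject same-day correlation, at 0.2, 0.5 and 0.8; two-sided 5% tests.

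**Single post-beverage time (also cortisol).**
- Change score: 1 + 1 - 2 rho = 2(1 - rho).
- Time 1 as covariate: 1 - rho².
- Ratio: 2/(1 + rho) = 2/1.2, 2/1.5, 2/1.8 = 1.67, 1.33, 1.11.
- Below rho = 0.5 the change variance 2(1 - rho) exceeds 1, so subtraction is then worse than ignoring Time 1.

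**Mean of Times 2-4, equal correlation.**
- Change score: (1 + 2 rho)/3 + 1 - 2 rho = (4/3)(1 - rho).
- Covariate: (1 + 2 rho)/3 - rho² = (1 - rho)(rho + 1/3).
- Ratio: 4/(1 + 3 rho) = 4/1.6, 4/2.5, 4/3.4 = 2.5, 1.6, 1.18.

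**Correlation falling geometrically, r per step.** With one slope common to all times, as in the model proposed below, the slope is c = (r + r² + r³)/3 = 0.083, 0.292, 0.651 at r = 0.2, 0.5, 0.8.
- Time 4: change 2(1 - r³) = 1.984, 1.750, 0.976; covariate 1 - 2cr³ + c² = 1.006, 1.012, 0.757; ratio 1.97, 1.73, 1.29.
- Mean of Times 2-4: with Vm = (3 + 4r + 2r²)/9, the ratio (Vm + 1 - 2c)/(Vm - c²) is 2.98, 1.95, 1.30.

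**Break-even.** Estimating the slope costs a little. With 2n - 4 error degrees of freedom, the covariate stops paying when [(1 + rho)/2][1 + 1/(2n - 6)] = 1. This gives rho = 0.90 at n = 12, 0.95 at n = 24 and 0.96 at n = 30. At n = 6 it would be 0.71.

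**Power, simulated.** Balanced six-sequence cross-over, n = 30, one beverage 0.5 within-subject SD from the other two, equal correlation, 2-df beverage test:

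| Outcome | rho | Change | Covariate |
|---|---|---|---|
| Single score | 0.2 | 31% | 48% |
| Single score | 0.5 | 47% | 59% |
| Single score | 0.8 | 87% | 90% |
| Mean of Times 2-4 | 0.2 | 44% | 84% |
| Mean of Times 2-4 | 0.5 | 65% | 86% |
| Mean of Times 2-4 | 0.8 | 97% | 99% |

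Null rejection of the beverage tests was 4.3-5.5%, so the gain is not bought with type I error.

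**Which tests are touched.** For two post-beverage times j and k on the same day, (Yk - Y1) - (Yj - Y1) = Yk - Yj. Time 1 cancels from the time main effect, from beverage by time and from contrasts between post-beverage times over the three change scores. A numerical check agrees. In one simulated data set the interaction F was 0.4235 on raw and on change scores, and the time F was 3.774 on both. If Time 1 is kept as a fourth level (its change is zero), the interaction equals the raw 3 × 4 interaction (0.4822 both ways), and Time 1 enters it with slope 1.

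**The case against.** The strongest reply is that the tests the plan names lose nothing. A reader might infer that change scores weaken the primary interaction. On the three scores actually defined they do not, because Time 1 cancels, and the same holds for follow-up contrasts between post-beverage times. That part of the reply stands. The interaction is affected only under the four-level reading, which the count of four times leaves open.

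A reader might also infer that cortisol is certainly tested this way and has no other test. The documents do not go that far. Nothing says that the saliva is assayed for cortisol, and two samples a day cannot fill a 3 × 4 layout, so no cortisol analysis is really specified. If pre and post are kept as two levels, a time test and an interaction can be formed, but that interaction is the same test as the beverage test on change. The cortisol point is therefore conditional on the assay. If cortisol is assayed, the one test of whether its pre-to-post change differs by beverage bears the loss.

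Nor may one infer bias. Subtracting a same-day baseline in a randomised cross-over is valid.

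Finally, the size is assumed. At rho 0.8 the power gain in the table is 2 to 3 points, and at very high rho it disappears. This stands too, and is why a range is given. Against it, rho concerns day-to-day deviations within a participant. Stable differences between participants do not raise it, so a high correlation across people is no assurance that rho is high.

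**Conclusion.** The point holds in a limited form. Change scores are valid, but for the beverage main effect, beverage contrasts at a single time and (if assayed) cortisol's beverage comparison they are less precise than day-specific Time 1 as a covariate, unless rho is near 0.9 or higher at sample sizes of 12 or more. For rho from 0.8 down to 0.2 and equal correlation, the excess variance is 11% to 67% at a single time and 18% to 150% for the mean of Times 2-4. Falling correlation makes it larger. These figures rest on equal variances and on assumed correlations; the documents cannot fix the actual loss. On the three-score reading this is lost efficiency outside the tests named as primary, so it is a cheap improvement and not a fault in validity.

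**What to change.** Analyse the Time 2, 3 and 4 scores in a mixed model with beverage, time, beverage by time, period and that day's Time 1 as covariate, with random effects for subject and for day within subject. Enter Time 1 as the subject's mean and the day's deviation from it, so that the slope used for beverage comparisons is the within-subject one. For cortisol, if assayed, model the post value on beverage, period and that day's pre value, split in the same way, with a random subject effect only.

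Two separate changes belong beside this one, and adjusting for Time 1 does not replace them. First, name the beverage effect among the primary tests: an effect of equal size at Times 2-4 does not appear in beverage by time over those scores (5% rejection in simulation). Second, reconcile the count of four times with the three change scores.

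The cost of the adjustment is analysis wording and one or two degrees of freedom. Time 1 is already collected on every test day, so no new data are needed.

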Stevia (Stevia rebaudiana) Leaf Extract, 97%	Trace amounts	Trace amounts	Trace amounts
Pomegranate Juice Concentrate ME-3605	Trace amounts	Trace amounts	Trace amounts
Masking Flavor Nat ME-1748	Trace amounts	Trace amounts	Trace amounts
Pomegranate-Berry Flavor Nat ME-2569	Trace amounts	Trace amounts	Trace amounts
Mint Flavor Nat WONF ME-2759	Trace amounts	Trace amounts	Trace amounts
Sodium Citrate	Trace amounts	Trace amounts	Trace amounts
Malic Acid	Trace amounts	Trace amounts	Trace amounts
Potassium Sorbate	Trace amounts	Trace amounts	Trace amounts

# Table 2

Time (minutes)	Event	Test Phase
0 – 36	Test battery	Trial 1
36-66	Beverage then seated rest	
66-102	Test battery	Trial 2
102-112	Rest	
112-148	Test battery	Trial 3
148-158	Rest	
158-194	Test battery	Trial 4

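### The change-score model lists three times but calls them four, and its tests of primary interest can miss a steady beverage effect or respond to drift alone

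*Combined protocol and SAP*

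**What the plan says.** All of the analysis text is in the section Analysis of outcomes. The model is a "two factor (3 beverages x 4 times) repeated measures ANCOVA on change scores". The levels of the time factor are then given as "Times 4, 3 and 2 minus Time 1 are the 4 Times".

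On the test that matters, the section says: "The primary interest will be whether there is a statistically significant main effect for time or interaction". The follow-up is described as "Focused contrasts between specific time points as follow up tests". Neither the beverage main effect nor a contrast between beverages is named.

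The Design statement crosses three treatments with four measured times, the first of them before the drink ("and Time (Time 1 (pre-beverage), Time 2, Time 3, Time 4"). Table 2 likewise has four test batteries. The entry "Beverage then seated rest" sits at 36-66 minutes, between the first battery and the second, so only Trials 2, 3 and 4 follow the beverage.

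**The concern.** There are two linked problems.

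- **The model is ambiguous.** Three differences from Time 1 are listed, yet the factor is twice said to have four levels. The two ways of resolving this give different degrees of freedom and an interaction test with different abilities.
- **The tests of primary interest do not match the question.** The trial compares beverages. Once the Time 1 value has been subtracted, a product that acts about equally at all three post-beverage batteries shows up mainly, and if exactly constant only, as a difference in the average change. That is the beverage main effect. A time main effect pools the three beverages and compares none of them.

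Two wrong conclusions could follow. A steady product effect could be reported as null on the primary tests. A time trend common to all beverages could be reported as a positive primary result.

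**Working it through.** **Step 1: count the levels.** The listed scores are Time 2 - Time 1, Time 3 - Time 1 and Time 4 - Time 1, which is three.

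- Three levels: time df = 3 - 1 = 2; interaction df = (3 - 1)(3 - 1) = 4.
- Four levels, as stated: time df = 4 - 1 = 3; interaction df = (3 - 1)(4 - 1) = 6.

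A fourth change score could only be Time 1 - Time 1, which is zero for everyone.

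**Step 2: what the subtraction does.** Let Y(i,j,k) be the score of subject i, beverage j, time k, and C(i,j,k) = Y(i,j,k) - Y(i,j,1). Within one subject-day the same number is removed at every k, so C(i,j,3) - C(i,j,2) = Y(i,j,3) - Y(i,j,2), and so on. The time and interaction tests, with their error terms, use only such within-day differences. Therefore:

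- with three levels they equal the tests on raw Times 2-4;
- with an all-zero fourth level they equal the tests of the raw 3 x 4 model.

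The beverage test on change scores is the same with or without the zero level, because that level only multiplies each day's mean by 3/4.

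**Step 3: a constant shift d in one beverage at Times 2-4.** Expected sums of squares per subject:

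- Three levels. Beverage means are 0, 0, d and the grand mean is d/3. Beverage: 3 x (1/9 + 1/9 + 4/9)d² = 2d². All time means are d/3, so time = 0. Interaction = 0.
- Four levels. Beverage means are 0, 0, 0.75d and the grand mean is 0.25d. Beverage: 4 x (0.0625 + 0.0625 + 0.25)d² = 1.5d². Time: 0.25d². The total is 3d² - 12 x 0.0625d² = 2.25d², so interaction = 2.25 - 1.5 - 0.25 = 0.5d².

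The zeros in the three-level case hold for any sample size, SD or d.

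**Step 4: size.** The documents give no sample size, SD, alpha, effect size or time profile, so there is no stated figure to reproduce. Assumed: n = 30, alpha 0.05, within-subject SD 1, of which 0% or 30% of the variance is shared within a day (residual variance s² = 1 or 0.7), no covariates, and one beverage differing by 0.5 SD on average over Times 2-4.

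For the flat shift:

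- Beverage main effect: a day's mean change has variance s²/3 + s² = 4s²/3. Noncentrality = n(2/3)d²/(4s²/3) = nd²/(2s²) = 30 x 0.25/2 = 3.75, or 3.75/0.7 = 5.36, on 2 and 58 df.
- Four-level interaction: n x 0.5d²/s² gives the same 3.75 or 5.36, but spread over 6 and 174 df.
- Three-level interaction: 0, on 4 and 116 df.

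Simulated power (20,000 trials per setting, standard error at most 0.35 points), shown as the value for s² = 1 / s² = 0.7. The noncentral F distribution gives the same figures to within a point.

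| Effect at Times 2, 3, 4 (SD) | Interaction, three levels | Interaction, four levels (= raw 3 x 4) | Beverage main effect on change scores |
|---|---|---|---|
| 0.5, 0.5, 0.5 | 5 / 5% | 24 / 35% | 37 / 51% |
| 0.4, 0.5, 0.6 | 7 / 8% | 27 / 39% | 37 / 51% |
| 0.25, 0.5, 0.75 | 20 / 28% | 40 / 57% | 37 / 51% |
| 0.3, 0.8, 0.4 | 22 / 31% | 42 / 59% | 37 / 51% |
| 0, 0.5, 1 | 70 / 86% | 79 / 92% | 38 / 51% |

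For the flat 0.5 SD shift at n = 20 and n = 40, the beverage main effect has 25-35% and 48-65%, the four-level interaction 17-23% and 32-46%, and the three-level interaction stays at 5%.

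**Step 5: time trend with no beverage difference.** With a drift of 0, 0.25, 0.5 SD at Times 2-4 in all three beverages and n = 30, three levels, the time noncentrality is 30 x 3 x 0.125/s² = 11.25 or 16.07. The time test is significant in 84-95% of trials. For 0, 0.15, 0.3 SD the rate is 40-54%. The four-level reading does not help: with a drift of 0, 0.3, 0.6 SD and residual SD 1, the rate is 95% with three levels and 98% with four.

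**The case against.** The strongest reply concerns how far the fault reaches. The plan says four levels twice, and the Design statement and Table 2 both have four times. If Time 1 minus itself is kept as a level, the interaction is that of the raw 3 x 4 model and does respond to a constant shift. This stands. A reader might infer that the primary tests can never detect a steady beverage effect. The documents do not support that without the condition that the three listed scores are the levels.

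A second reply is that the two-factor model produces the beverage main effect anyway. This also stands, so it would be wrong to infer that the plan provides no test between beverages. The fault is that the beverage main effect is not named as of primary interest. Moving to it after null results on the named tests would be a choice made with the data in view.

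Third, real effects are rarely exactly flat, and the batteries run from 66 to 194 minutes. Agreed: the flat profile is the extreme case, and for a steep rise even the three-level interaction beats the beverage main effect. For the same reason, a reader should not conclude that the beverage main effect is the only sound primary test. The four-level interaction has more power in three of the five profiles above, and the documents give no profile by which to choose.

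None of these replies rescues the time main effect, which compares no beverages under either reading.

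**Conclusion.** The point holds in conditional form and should be corrected before analysis.

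- **Certain from the text:** three scores are called four, and neither the beverage main effect nor a between-beverage contrast is named.
- **Certain by algebra, if the three listed scores are the levels:** both tests of primary interest reject at no more than the alpha level for a constant post-beverage difference.
- **If an all-zero level is meant:** the interaction keeps some power for that difference, though less than the beverage main effect.
- **Under either reading:** a significant time effect is not evidence that any beverage differs.

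The percentages are illustrations that rest wholly on assumed inputs. The algebra and the miscount do not depend on them.

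**What to change.** 1. State whether the time factor has three or four levels, and make the model, the list of scores and the degrees of freedom agree.
2. Remove the time main effect as a primary test.
3. Name in advance, for each outcome, one primary test that compares beverages. Either option is acceptable:
   - (a) 3 beverages x 3 post-beverage change scores, with the beverage main effect primary and beverage by time secondary. If both are to be primary, split alpha or use one joint test. Testing each at 0.05 gives about 9.5-9.9% false positives per outcome; 0.025 each gives 4.8-5.0%. At n = 30 the split has 29-41% power for the flat profile and 70-87% for 0, 0.5, 1 SD.
   - (b) Raw scores at Times 1-4 (3 x 4), with beverage by time primary.
4. Make the follow-up contrasts between beverages at each post-beverage time.

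The price of (a) is less power when the effect rises or falls steeply across Times 2-4. The price of (b) is less power when it is flat. The sponsor's expectation of the time course should decide, and should be written down before the data are seen. The change takes a few sentences in the analysis section, with no added visits or samples.
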